6.2 Medication Management

6.2.1 Labeling, Packaging and Distribution

The study medication assigned to each subject number will be determined by a computer-generated randomization schedule. Study medication is labeled and packaged, according to the random code, so that neither the subject nor the investigator can identify the treatment.

[REDACTED]

All study medications will be supplied to the subjects in 0.47 gram tubes. Each subject's treatment unit will consist of one kit box containing [REDACTED] tubes of study medication. The outer label of the box will not contain any information that could identify the treatment group to which the subject was assigned. The kit box labels will include the name of Perrigo Israel Pharmaceuticals, Ltd., study protocol number, subject number and initials, directions for use and storage, and warnings: "For Topical Use Only." "Not for Ophthalmic, Oral, or Intravaginal Use" and "Caution: New Drug - Limited by Federal (or United States) law to investigational use."

The tear-off portion of each label contains the identity of the medication in the tube. The investigator will not remove the occluding layer of the label unless absolutely necessary to provide medical treatment to a subject in an emergency and preferably with prior authorization from Perrigo or designee whenever possible. If the occluded portion of the label is removed, each involved subject(s) will be discontinued from the study and the reason will be noted on the source document and eCRFs.

The tear-off portion has an adhesive backing to affix to the study medication dispensing log that will be maintained at the investigator site. The individual boxes are numbered sequentially and should be dispensed in order.

6.2.2 Retention Samples

Each investigational site where study medication is dispensed to at least one subject will be required to randomly select [REDACTED] retain samples. The retention samples must be stored under labeled conditions [in a refrigerator at 36°-46°F (2-8°C); excursions permitted to 32°-59°F (0°-15°C)] even after the study has concluded. The investigator will maintain one randomly selected block of study medication for each shipment of study medication received. As per the Code of Federal Regulations Part 21, Section 320.38(e), "Each reserve sample shall be stored under conditions consistent with product labeling and in an area segregated from the area where testing is conducted and with access limited to authorized personnel. Each reserve sample shall be retained for a period of at least 5 years following the date on which the application or supplemental application is approved, or, if such application or supplemental application is not approved, at least 5 years following the date of completion of the bioavailability study in which the sample from which the reserve sample was obtained was used." The investigator will store the retain sample study medication until such time as notification is received from Perrigo that the samples are no longer required.

6.2.3 Storage and Test Article Accountability

Study articles used to conduct this study will be maintained under adequate security by the investigator or designee. Study test articles will be stored in a refrigerator at a temperature of 36°- 46°F (2-8°C); excursions permitted between 32°- 59°F (0°-15°C) in a secured area. Subjects must be instructed to keep the study medication refrigerated at home. Each investigator site will ensure that the temperature of study drug is monitored and recorded throughout the study. The medication should not be frozen, kept away from heat and kept tightly closed. The

Protocol No: PRG-NY-15-002

investigator will not supply study test articles to any person not enrolled in this study, or to any physician or scientist except those named as sub-investigators.

The clinic personnel at each investigator site will keep a running inventory of study test articles dispensed that will include subject numbers assigned and the date each is dispensed and used. A study medication accountability form will be provided to the investigator to document all medications received, dispensed by and used by each subject. At the conclusion of the study all unused, partially used, and empty containers must be inventoried by the monitor and returned to Perrigo or designee, for destruction, except for the retention samples that must remain at the Investigator site.

6.2.4 Randomization

Randomization will be performed according to a computer generated randomization scheme where the treatment group designation has been assigned to the subject number. The treatment designation will remain blinded until the final database is closed. An independent third party will hold the randomization code throughout the study. The randomization scheme will be a block randomization, with each [REDACTED] subjects assigned to Test: Reference: Placebo [REDACTED].

6.2.5 Procedure for Breaking the Blind

The investigator, staff at the study site, study monitors, and data analysis/management personnel are blinded to the subject assignment. In the event of an emergency, the specific subject treatment may be identified by removing the overlay of the blinded label for each subject at each investigator site, which is attached to the study medication log. However, every effort should be made to maintain the blind. **The investigator must not scratch off the occluding layer of the label unless absolutely necessary to provide medical treatment to a subject in an emergency situation. When possible, the investigator site should inform Perrigo or designee.** The reason for breaking the blind must be clearly documented in the source documentation and eCRFs and the subject discontinued from the study.

7. ADVERSE REACTIONS

The potential adverse reactions of generic Ingenol Mebubate Topical Gel 0.05% are anticipated to be similar to those observed in Picato[®] Topical Gel (Ingenol Mebutate Topical Gel 0.05%). The most common adverse reactions related to treatment with Picato[®] Topical Gel include local skin reactions, application site pain, application site pruritus, application site irritation, and nasopharyngitis. Eye disorders, including severe eye pain, eyelid edema, eyelid ptosis, and periorbital edema can occur after exposure. Severe local skin reactions such as vesiculation/pustulation, erosion/ulceration can occur.

7.1 Departure from the Protocol for Individual Subjects

When an emergency occurs requiring a departure from the protocol for a subject, departure will be only for that subject. In such circumstances, the investigator or other physician in attendance will contact the Medical Monitor or Perrigo by telephone and follow up with a written description within one day. The overseeing IRB should also be notified.

7.2 Definitions

An adverse event (AE) is defined as any untoward medical occurrence in a patient administered a medicinal product and which does not necessarily have to have a causal relationship with this treatment. An adverse event can therefore be any unfavorable and unintended sign (for example, an abnormal laboratory finding), symptom, or disease temporally associated with the use of a medicinal product, whether or not considered related to this medicinal product.

A serious adverse event (SAE) is an adverse event that results in any of the following outcomes:

- death
- life-threatening event (i.e., the subject was, in the opinion of the investigator, at immediate risk of death from the event as it occurred. It does not include an event that, had it occurred in a more severe form, might have caused death)
- requires in-subject hospitalization or prolongs hospitalization
- a persistent or significant disability/incapacity or substantial disruption of the ability to conduct normal life functions
- congenital anomaly/birth defect
- Other adverse events that may be considered serious when, based upon appropriate medical judgment, they may jeopardize the patient or subject or may require medical or surgical intervention to prevent one of the previously listed outcomes.

Immediately Reportable Adverse Events (IRAE): Any serious AE or any AE that necessitates discontinuation of study medication, including pregnancy.

Unexpected Adverse Event: An unexpected event is any adverse drug experience, the specificity or severity of which is not consistent with the current approved product labeling (package insert, Appendix D) for the study medication, the Investigator's Brochure, or as described in the clinical protocol and consent materials.

Intensity of Adverse Events: The maximum intensity of an AE during a day should be recorded on the eCRF. If the intensity of an AE changes over a number of days, then separate entries should be made having distinct onset dates for the changes in severity.

Mild - AEs are usually transient, requiring no special treatment, and do not interfere with subject's daily activities.

Moderate - AEs typically introduce a low level of inconvenience or concern to the subject and may interfere with daily activities, but are usually ameliorated by simple therapeutic measures.

Severe - AEs interrupt a subject's usual daily activity and traditionally require systemic drug therapy or other treatment.

Causal Relationship to Study Medication: The following criteria should be used in assessing the apparent causal relationship of an AE to study medication.

Definitely - The AE:

- follows a reasonable temporal sequence from study medication administration
- abates upon discontinuation of the study medication (dechallenge)
- is confirmed by reappearance of the reaction on repeat exposure

Probably - The AE:

- follows a reasonable temporal sequence from study medication administration
- abates upon discontinuation of the study medication (dechallenge)
- cannot be reasonably explained by the known characteristics of the subject's state

Possible - The AE:

- follows a reasonable temporal sequence from study medication administration
- but that could readily be produced by a number of other factors

Unlikely - The AE:

- follows a reasonable temporal sequence from study medication administration
- could have been produced by either the subject's clinical state or by study medication administration

Not related - The AE:

- does not have a reasonable temporal association with the administration of study medication
- has some other obvious explanation for the event

7.3 Eliciting and Reporting of Adverse Events

The investigator will periodically assess subjects for the occurrence of adverse events. In order to avoid bias in eliciting adverse events, the subject or parent/legally authorized representative should be asked a non-specific question (e.g., "How have you been feeling since your last visit?") to assess whether any AE has been experienced since the last visit. All adverse events (as defined in [Section 7.2](#)), either observed by the Investigator or one of his/her medical collaborators, or reported by the participant spontaneously, or in response to direct questioning, will be reported and documented in the source and the study reporting forms. When reporting an adverse event, the Investigator must assign a severity grade to each event and declare an opinion on the relatedness of the event to the study medication or procedure. Serious or unexpected adverse events must be reported to Perrigo and [REDACTED] **within 24 hours** of when the Investigator first learns of the occurrence of the event.

Adverse events will be documented in source and recorded in a timely manner on eCRFs. Adverse events (i.e., worsening of Actinic Keratosis*) that are identified at the last assessment visit (or the early termination visit), must be recorded on the AE eCRF with the status of the AE noted.

** Worsening of the subject's Actinic Keratosis may be expected from application of the study medication. Therefore, this will not be considered an AE unless one or more of the following occurs: 1) alternative treatment required; 2) subject is discontinued by the Principal Investigator for worsening of AK.*

Adverse event reporting begins from the signing of informed consent/assent. Adverse events should be followed until resolved or 30 days after the final study treatment. In any case, serious adverse events that are not resolved or considered to be chronic within 30 days of the final study treatment must be followed by the investigator until they become resolved or are considered to be chronic (stabilized for at least 30 days). All events that are ongoing at this time will be recorded as ongoing on the eCRF.

7.3.1 Expedited Reporting Responsibilities of the Study Center

For any serious or unexpected adverse event, Perrigo must be notified **within 24 hours** of when the Investigator first learns of the occurrence of the event. Expedited reporting requirements for serious adverse events are described below. Adequate information must be collected with supporting documentation to complete a standard report for submission to Perrigo. The adverse event term on the AE eCRF and the SAE report should agree exactly. Special attention should be given to recording hospitalizations and concomitant medications.

Subjects with unresolved adverse event(s) or serious adverse event(s) should be followed by the investigator until the events are resolved, events determined to be chronic or the subject is lost to follow-up. Resolution means the subject has returned to the baseline state of health, or the investigator does not expect any further improvement or worsening of the adverse event. The investigator should continue to report any significant follow-up information to Perrigo up to the point that the event has resolved. Any serious adverse event reported by the subject to the investigator that occurs within 30 days after the last assessment, and are determined by the investigator to be reasonably associated with the use of the study medication, should be reported to Perrigo within 24 hours of when the Investigator first learns of the occurrence of the event.

When reporting a serious adverse event (SAE) the Investigator (or the designated staff) will promptly report any serious adverse event or pregnancy by telephone to [REDACTED] immediately after the investigator becomes aware of the event. An SAE form should be completed and sent by fax, email, or overnight courier to [REDACTED] within 24 hours of knowledge of the event by the site. In many cases, only preliminary information will be available. Appropriate follow up information should be sought (hospital discharge summaries, operative reports etc.) and a follow up SAE report form submitted. A designation of causality from the study medication should always be included with a follow up report. Assess and report the causality of the event.

7.3.2 Submitting an Expedited Safety Report to the IRB

Protocol No: PRG-NY-15-002

Once [REDACTED] receives all supporting documentation for the reported event, the Medical Monitor, in conjunction with Perrigo, will determine if the safety report is eligible for expedited review. [REDACTED] will log the initial event and will notify Perrigo that an event has been reported within 1 business day after initial receipt. [REDACTED] will complete the review of the event, enter information into their safety database and generate the report. This form, as well as other supporting documentation, will be forwarded to [REDACTED] Medical Monitor for review. [REDACTED] will finalize the report and distribute it to Perrigo within 2 days after initial receipt. When expedited safety reporting to regulatory authorities is indeed required, the Investigator should review and update any newly available materials at once. Follow-up queries may be issued to the study center to further clarify the event.

Each expedited safety report will routinely include a brief cover memorandum, the completed report, and any additional pertinent information recommended by [REDACTED], Perrigo, or study Medical Monitor. Once the report is assembled, the Principal Investigator must submit the expedited safety report to the IRB within the required reporting timeframe. Follow-up reports should be submitted when requested or when pertinent information becomes available.

When a Principal Investigator receives an expedited safety report from [REDACTED] or Perrigo detailing adverse events occurring at other study centers under this protocol, it must be promptly submitted to the study center's IRB. The Principal Investigator must retain a copy of such reports as submitted to their IRB in the site's study Regulatory Binder.

7.4 SAE & AEs Requiring Discontinuation of Study Drug, including Pregnancies

ANY SAE, WHICH OCCURS AFTER A SUBJECT HAS ENTERED THE STUDY, WHETHER OR NOT RELATED TO STUDY MEDICATION, MUST BE REPORTED TO [REDACTED] AND PERRIGO IMMEDIATELY (WITHIN 24 HOURS) VIA TELEPHONE OR FACSIMILE. IF INITIALLY REPORTED VIA TELEPHONE, THIS MUST BE FOLLOWED-UP BY A FACSIMILE OF THE WRITTEN SAE REPORT WITHIN 24 HOURS OF THE CALL TO [REDACTED].

Non-serious events that require discontinuation of study medication (including laboratory abnormalities) should be reported to Perrigo immediately and within 1 working day. Subjects who discontinue due to experiencing adverse events should be followed clinically until their health has returned to baseline status, or until all parameters have returned to normal. It is expected that the investigator will provide or arrange appropriate supportive care for the subject.

A subject who experiences a severe adverse event related to study drug will be discontinued from the study.

The notification about any serious adverse event should be directed to:

[REDACTED]
[REDACTED]

[REDACTED]

[REDACTED]

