5.15 Protocol Deviations/Violations

This study will be conducted as described in this protocol except for an emergency situation in which the protection, safety, and well-being of the subject requires immediate intervention, based on the judgment of the investigator or a responsible, appropriately trained and credentialed professional(s) designated by the investigator. In the event of a significant deviation from the protocol due to an emergency, accident or mistake, the investigator or designee must contact Perrigo/[REDACTED] contacts in Section 14 ([Appendix A](#)) at the earliest possible time.

[REDACTED]

[REDACTED]

[REDACTED]

[REDACTED]

[REDACTED]

[REDACTED]

[REDACTED]

Subjects with any variation from the protocol that would not interfere with the effect of or the accurate assessment of the assigned study treatment, may be included in both PP and mITT analyses.

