5.16 Subject/Treatment Compliance

Subjects will apply the medication to the designated treatment area at approximately the same time once daily for 2 consecutive days. [REDACTED]

[REDACTED]. Compliance will be determined from the diary card, in which the subject will be instructed to record all applications made or missed. The first and last dates of treatment should be recorded in the source document and eCRFs. The total number of applied and missed applications should also be recorded. Applications will be considered missed if the study medication was not applied on Day 1 or Day 2 of the treatment period. Subjects will be considered compliant if they apply both daily doses on study Days 1-2. Subjects will be considered non-compliant if one (1) or more doses are missed. The study medication tube will be collected by the study site at appropriate visits or early termination.

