5.17 Discontinuation/Withdrawal of Study Subjects

Subjects will be removed from the study for any of the following reasons:

- The subject withdraws his or her consent/assent for any reason.
- The subject's condition has worsened to the degree that the investigator feels it is unsafe for the subject to continue in the study.
- Subject did not meet entry criteria.
- The subject's medication code is unblinded.
- An adverse event (AE) including inter-current illness, occurs for which the subject desires to discontinue treatment or the investigator determines that it is in the subject's best interest to be discontinued.
- The subject is lost to follow-up. The investigator will document efforts to attempt to reach the subject twice by telephone and will send a certified follow-up letter before considering that subject lost to follow-up. All attempts must be thoroughly recorded.
- The subject becomes pregnant during the course of the trial.
- Lack of efficacy (treatment failure) (subject's own withdrawal or investigator removal from study)
- Investigator Discretion

[REDACTED]

Protocol No: PRG-NY-15-002

- Significant protocol violation or non-compliance with the study protocol that could interfere with the effect or accurate assessment of the assigned study treatment.

A subject will not be allowed to re-enroll in the study after they have been discontinued.

The reasons for a subject being discontinued will be documented in the source document, eCRFs and the enrollment log.

If a subject is discontinued from the study for any reason, the Visit 4/ Day 57 End of Study Visit/Early Termination Visit procedures should be completed and any outstanding data and study medication should be collected. Data, in addition to the primary reason for discontinuation and the date of removal, will be recorded in the source document and the End of Study eCRF.

[REDACTED]

[REDACTED]

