8.1.2 Planned Analysis

All subjects who received study medication will be evaluated for safety. The efficacy analysis will be conducted on both the PP and the mITT subject populations. Two-sided hypothesis testing will be conducted for tests. Resulting p-values less than 0.05 will be considered statistically significant. No adjustments of p-values for multiple comparisons will be made. No interim analyses are planned. SAS software will be used for all data analyses and tabulations.

The treatment response will be summarized by treatment group for the end-of-study evaluation. The primary efficacy endpoints will be the proportion of subjects with clinical response of success defined as complete clearance (absence) of all clinically visible Actinic Keratosis lesions identified at the Baseline visit and no new Actinic Keratosis lesions in the treatment area at Visit 4/Day 57.

[REDACTED]

[REDACTED]

[REDACTED].

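### Protocol 7.4 removes subjects from the study for any severe drug-related AE; after the Day 2 dose this withholds no drug and gives up an obtainable Day 57 lesion count

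*Protocol*

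**What the plan says.** Protocol 7.4 states: "A subject who experiences a severe adverse event related to study drug will be discontinued from the study." Section 7.3 leaves the grading to the investigator ("the Investigator must assign a severity grade to each event and declare an opinion on the relatedness of the event"), but once an event is graded severe and related, 7.4 fixes the consequence. Severe is an intensity grade in Section 7.2, defined separately from serious.

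The surrounding text is as follows.

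- **Dosing:** one application on each of Days 1 and 2, none later (Protocol 5.11, 5.16).
- **Endpoint:** clearance of all lesions, with no new ones, at Visit 4/Day 57, window ±2 days.
- **Lesion counts:** at baseline, Visit 4 and any unscheduled visit (Protocol 5.9). Day 3 and Day 29 are not count visits.
- **On leaving early:** Protocol 5.17 says the Visit 4 "End of Study Visit/Early Termination Visit procedures should be completed", whatever the reason.
- **Analysis sets:** "The efficacy analysis will be conducted on both the PP and the mITT subject populations" (Protocol 8.1.2). SAP 4 requires at least one post-baseline efficacy assessment for mITT. For PP it requires Visit 4 in window, or discontinuation for treatment failure with full compliance.
- **Missing data:** LOCF in mITT (SAP 5.2).

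Two items in 5.17 are related. The AE item applies when an event "occurs for which the subject desires to discontinue treatment or the investigator determines that it is in" the subject's best interest to leave. The non-compliance item reads "Significant protocol violation or non-compliance with the study protocol that could interfere with the effect" or the accurate assessment of treatment, and 5.16 adds: "Subjects will be considered non-compliant if one (1) or more doses are missed."

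**The concern.** With two days of dosing and an eight-week endpoint, stopping drug and leaving the study are different acts. Section 7.4 treats them as one. After Day 2 the rule cannot reduce exposure, and its only effect is to end participation.

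Safety cover is not what is lost. Clinical follow-up of AEs, the early termination procedures and the unsafe and best-interest grounds for removal all exist elsewhere in the protocol. What is lost is a primary outcome that could have been observed, in subjects selected by a post-randomization drug effect. Both efficacy populations are touched. In addition, SAP 5.6 tabulates site reactions by visit and SAP 5.2 uses available data, so a subject removed before Day 29 also drops out of the scheduled Day 29 and Day 57 safety tables.

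A smaller, separate point concerns the gap between the two doses. The AE item in 5.17 removes from the study a subject who only wants to stop treatment, and the non-compliance item could remove one who misses dose 2 because of an AE. No contradiction between 7.4 and 5.17 is claimed.

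**Working it through.** **1. When the rule withholds nothing.** The last dose is on Day 2 and the Visit 4 window is Days 55 to 59. From Day 3 to Day 54, that is 54 − 3 + 1 = 52 of the 57 study days, removal withholds no drug and forfeits the Day 57 count. Removal before Day 29 costs the Day 29 and Day 57 assessments; removal after Day 29 costs Day 57 only; an event first found at Visit 4 costs nothing.

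**2. How far the rule reaches.** Under Protocol 5.10 the six listed site reactions are AEs only if they cause a drug interruption, study discontinuation or new medication. A listed reaction that is newly medicated can therefore become an AE and, if graded severe and related, trigger 7.4. Pain and pruritus are always AEs. The rule covers all three arms.

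**3. What the analysis does with a removed subject.** The early termination count is usually the only post-baseline count. In mITT it becomes the Day 57 value; with no post-baseline efficacy assessment the subject leaves mITT. A fully dosed subject removed for an AE before the window is outside the readable PP definition, unless the reason is classed as treatment failure.

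**4. Size.** The plan's readable text has no figure to reproduce: the sample size section is redacted and no event rates are given. Every input below except the margin is assumed.

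- *p* = 45%, overall Day 57 clearance
- *q* = 30% to 70%, Day 57 clearance of removed subjects had they stayed
- *e* = 0% to 100%, proportion of removed subjects with a zero count at early termination
- *rT*, *rR* = proportions removed in Test and Reference
- margin = 20 points (Protocol 8.1.4)

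mITT shift in Test minus Reference = (*rT* − *rR*)(*e* − *q*), taking every removed subject to have an early count:

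- 5% vs 2%, *q* = 0.70, *e* = 0: 0.03 × (−0.70) = −2.1 points
- 5% vs 2%, *q* = 0.30, *e* = 1: 0.03 × 0.70 = +2.1 points
- 5% vs 2%, *e* within 0.30 of *q*: at most 0.03 × 0.30 = 0.9 points
- 3% vs 2%: at most 0.01 × 0.70 = 0.7 points either way
- equal removal, same *e* and *q* in both arms: 0
- 5% removed in both arms, *e* − *q* differing by 0.20 between arms: 0.05 × 0.20 = 1.0 point

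PP shift = (*p* − *rT q*)/(1 − *rT*) − (*p* − *rR q*)/(1 − *rR*):

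- 5% vs 2%, *q* = 0.70: 0.415/0.95 − 0.436/0.98 = 0.4368 − 0.4449 = −0.81 points
- 5% vs 2%, *q* = 0.45: 0
- 5% vs 2%, *q* = 0.30: 0.435/0.95 − 0.444/0.98 = 0.4579 − 0.4531 = +0.48 points
- 3% vs 2%, *q* = 0.70: 0.4423 − 0.4449 = −0.26 points
- 3% vs 2%, *q* = 0.30: 0.4546 − 0.4531 = +0.16 points

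Reversing the imbalance reverses the signs. Against the margin, 2.1/20 = 10.5% and 0.7/20 = 3.5%.

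**The case against.** The strongest reply has four parts.

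1. **The effect is small and its direction unknown.** The 2.1-point limits need *e* at 0 or 1 with *q* at its extreme. This stands, and it is why the point is put as an improvement only.
2. **Not all removals are due to 7.4.** Protocol 5.17 already allows removal for an AE at the subject's wish or on the investigator's judgment, and severe related cases are the likeliest to meet those grounds. The fix keeps most of those exits, so only part of the assumed removal rate is recoverable. This stands: the figures above are ceilings on the gain.
3. **PP may gain little.** Severe events often need treatment, and that treatment may itself be a significant violation under item (e) of the SAP's PP definition. The PP figures assume that every removed subject would otherwise have qualified, and some retained Day 57 counts would follow AE treatment. Both limits stand. Even so, such a count is the outcome at the planned time, which an early count is not.
4. **Other text may cover it.** Protocol 5.12.6 lets a subject whose condition worsens to an unsafe degree be discontinued as a treatment failure, which can preserve PP status. That fits worsening disease, not severe local or systemic drug reactions. Redacted text in 5.12, 5.15, 5.17 and 8.1 may add handling rules, and the readable text does not say when the early termination count is made. Nothing readable relaxes the 7.4 sentence.

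The rule can also be defended as conservative protection. During the dosing period that is fair for the drug; after Day 2 it no longer is.

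**Conclusion.** The concern holds. The rule is mandatory, has no time limit and acts on study participation; after Day 2 it protects no one from further exposure, and before the window it replaces an obtainable Day 57 outcome with an early one in mITT and, on the readable text, removes the subject from PP unless treatment failure is the reason.

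That reading is firm. The size is not, because event rates, clearance rates and sample size are not available. On the assumed inputs the shift in Test minus Reference is at most 2.1 points in mITT and 0.8 in PP, and 0.9 or less in mITT if early and Day 57 clearance among removed subjects are within 30 points of each other. It is probably small against the 20-point margin. The change should be made because it is cheap and the loss avoidable, not because the equivalence conclusion is at risk.

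**What to change.** Amend Protocol 7.4 to say that a severe AE related to study drug stops any remaining application but is not by itself a reason to leave the study. Subjects stay to Day 29 and Day 57 unless they withdraw consent, or the investigator judges that staying is unsafe or not in their best interest. Any treatment needed for the AE is allowed and recorded. PP status is then decided under the existing violation rules: item (e) of the SAP's PP definition, and Protocol 5.15, under which subjects with deviations that do not interfere with treatment effect or assessment "may be included in both PP and mITT analyses".

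Two secondary edits to 5.17: make the AE item distinguish stopping treatment from leaving the study, and state that a dose missed because of an AE is not by itself grounds for removal as non-compliance. Such a subject stays outside PP but can have an observed Day 57 result in mITT. Keep the clinical follow-up and early termination procedures for those who do leave.

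The cost is three short edits by amendment and a consistency check of the redacted text in 5.15, 5.17 and 8.1.1. No visits are added, since Day 29 and Day 57 are already scheduled. The downside is that a few symptomatic subjects are followed longer and some Day 57 counts may come after AE treatment.
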